5.8.5. Subgroup Analyses

The mITT population is defined as all randomized subjects who receive at least 1 dose of IMP and have both an eDiary baseline compliance $\geq 20\%$ and at least 1 post baseline entry in the seizure diary during maintenance phase. To further assess the impact of the eDiary compliance, sensitivity analyses based on the subgroup with a baseline compliance $\geq 50\%$ and a maintenance phase compliance $\geq 50\%$ may be conducted if the sample size allows.

In addition, the following subgroup analyses will be conducted:

- 1. subjects with baseline eDiary compliance $\geq 80\%$.
- 2. subgroup analysis of baseline disease characteristics based on seizure frequency, defined: Low frequency= up to 20 seizures a week; High frequency = 21 and above, including all subjects with "uncountable" seizures will be conducted.

5.9. Key Secondary Efficacy Analyses

5.9.1. Derivation of Key Secondary Efficacy Endpoints

5.9.1.1. Change in Log-Transformed Seizure Frequency from Baseline

The 7-day adjusted seizure frequency will be log-transformed using the convention ln(X+1), where X represents the focal onset seizure frequency. This will be summarized for the Titration Phase and Maintenance Phase.

5.9.1.2. 50% Responder

Responder status (yes or no) for a subject is determined by the percent reduction in 7-day adjusted seizure frequency during the Maintenance Phase from Baseline. A subject is defined as

a 50% responder if subject has at least a 50% reduction in the focal onset seizure frequency during the Maintenance Phase relative to the Baseline Period.

5.9.2. First Key Secondary Estimand

The key research question for the first secondary efficacy variable will be addressed with an estimand based on the following attributes:

- 1. Treatments: treatments as randomized regardless of the actual treatment received.
- 2. Target study population of interest: subjects in the modified intent-to-treat (mITT) population.
- 3. Endpoint (variable) of interest: change from baseline in focal onset seizure frequency in logarithmic scale.
- 4. Population level summary of interest: estimated mean difference between CVL-865 treated and placebo subjects in change from baseline in focal onset seizure frequency per week in logarithmic scale during the Maintenance Phase.
- 5. Strategy for Intercurrent events (ICEs): a hypothetical strategy will be used to address intercurrent events (ICEs) of potential death, and treatment discontinuations. The data after treatment discontinuations will typically be missing or be treated as missing even if collected. Under the hypothetical strategy, these missing values as the result of ICEs of discontinuation will be assumed to follow the observed trajectory of the subject and thus the endpoint will include only eDiary based response data that occur before discontinuation of treatment. It should be noted that the use of protocol defined rescue medication will not be considered as an ICE.

5.9.3. Main Analytical Approach for First Key Secondary Endpoint

The change from baseline in log-transformed seizure frequency will be analyzed using an ANCOVA, including treatment as a factor and the log-transformed baseline focal onset seizure frequency per week as a covariate. The comparisons between the treatment groups will be based on the LS Mean difference between each CVL-865 dose group and placebo with corresponding 90% CI and P-value.

The LS Mean and 90%CI for each treatment group in log scale will be exponentiated to derive the model-estimated mean percent change from baseline using the following formula:

Estimated Mean % Change from Baseline=100*[1-exp(LSMean)]

The percent reduction relative to placebo and 90%CI will be constructed by exponentiating the LSMean difference and 90%CI between each CVL-865 treatment group and placebo from the ANOCOVA model using the following formula:

$$\% \frac{Reduction}{Placebo} = 100 * [1 - \exp(LSMean_{CVL-865} - LSMean_{Placebo})]$$

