# 9.4.1 Efficacy Analyses

Seizure frequency is defined as the total number of focal onset seizures over the treatment period of interest divided by the total number of days with no missing seizure counts in the corresponding period multiplied by 7.

The primary efficacy endpoint is the Rratio over the Maintenance Phase. This is calculated as Rratio= $(T-B)/(T+B) \times 100$ , where T represents the seizure frequency rate per week in the Maintenance Phase and B represents the seizure frequency rate per week in the Baseline Period. The Rratio is between -100 and 100. Negative values will indicate reduction in seizure rate and positive values indicate increase in seizure rate during treatment.

Values of Rratio will be analyzed for the mITT population using an analysis of covariance model, including treatment and the baseline seizure frequency per week as a covariate. This estimand will include response data that occur before discontinuation of treatment. The differences between the treatment groups will be based on the least square mean (LSMean) difference between each CVL-865 group and placebo. A separate comparison of the combined CVL-865 groups and placebo may be conducted. The corresponding 95% confidence interval (CI) will be presented. Sensitivity analyses will be conducted by including all available data (de facto estimand).

A key secondary efficacy endpoint is the change from baseline in focal onset seizure frequency per week over the Maintenance Phase. These data will be log-transformed using the convention ln(X+1), where X represents the focal onset seizure frequency. The log-transformed values will be analyzed using an analysis of covariance model, including treatment as a factor and the log-transformed baseline focal onset seizure frequency per week as a covariate. The differences between the treatment groups will be based on the LSMean difference between each CVL-865 group and placebo. The percent reduction relative to placebo will be constructed by exponentiating the LSMean difference between each CVL-865 treatment group and placebo using the following formula:

$$\% \text{Reduction/Placebo} = 100 \frac{\exp(LSMean_{placebo}) - \exp(LSMean_{CVL-865})}{\exp(LSMean_{placebo}) - 1}$$

The corresponding 95% CI will be calculated. A secondary analysis of this endpoint will be conducted using a Poisson Regression model on the untransformed data.

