5.9.4. Sensitivity Analyses

The sensitivity analyses to assess the impact of low eDiary compliance and that of discontinuation potentially related to treatment described in Section 5.8.4 for the primary estimand will also be performed for the key secondary efficacy estimand.

Two additional sensitivity analyses will be performed to assess the impact of the logarithmic transformation ln(X+1) of seizure frequency. The first one will be based on a slightly modified logarithmic transformation ln(X+0.1). This sensitivity analysis is to assess if the correction for zero in seizure frequency may have undue effect on other low seizure frequencies. In addition, the percent change from baseline in seizure frequency in Titration Phase and Maintenance Phase will also be analyzed using a nonparametric approach (in the original scale) of Wilcoxon rank sum test followed by the Mann-Whitney test for the comparison of each active treatment group to placebo.

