5.9.5. Subgroup Analysis

The following subgroup analyses will be conducted:

- 1. subjects with baseline eDiary compliance $\geq 80\%$.
- 2. subgroup analysis of baseline disease characteristics based on seizure frequency, defined: Low frequency= up to 20 seizures a week; High frequency = 21 and above, including all subjects with "uncountable" seizures will be conducted.

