5.11. Other Efficacy Analyses

5.11.1. Other Secondary Efficacy Endpoints

Other protocol-defined secondary efficacy endpoints will be summarized using descriptive statistics by treatment group and visit, if appropriate. Statistical analysis method for each endpoint is described below in Table 11. Statistical comparisons for each endpoint will be constructed without adjustment for multiple endpoints.

Table 11:	Summary of Other Secondary Efficacy Analyses

Endpoint	Analysis Population	Analysis Method
Seizure Freedom	mITT	Seizure freedom is defined as no seizures during the maintenance period. A logistic regression model with treatment as a fixed effect will be used. Odd ratios will be constructed for each CVL-865 treatment dose group compared with placebo and will be summarized with 90% confidence intervals. Should a logistic regression model fail to converge, paired Fisher's exact tests will be used instead.
Seizure Rate over Time	mITT	Seizure rate over time during the maintenance period will be analyzed using an MMRM. Only focal onset seizure will be included in this analysis. Data will be log-transformed using the convention ln(X+1), where X represents the seizure rate at each time point. Treatment group (CVL-865 7.5 mg, CVL-865 25 mg, or placebo), visit, and the interaction between treatment group and visit will be included as fixed factors in the MMRM, and log-transformed baseline rate will be included as a covariate. Subject will be included as a random effect, and an unstructured covariance structure will be used for the repeated measures. The difference between each CVL-865 level versus placebo at each visit will be estimated based on the LSMeans from the MMRM. The model estimated mean percent change from baseline and percent reduction versus placebo at each visit will be derived from back-transformed statistics the same way as described in Section 5.9.3 . A Mann-Whitney U test will also be used to compare each treatment level versus placebo at each visit.

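### SAP 5.9.3 back-transforms ln(X+1) without removing the added 1, so its percent reductions understate the reduction in seizures

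*SAP*

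**What the plan says.** SAP 3.1.1 scales seizure counts to 7 days, so X is a weekly rate. SAP 5.9.1.1 defines the endpoint: "The 7-day adjusted seizure frequency will be log-transformed using the convention ln(X+1), where X represents the focal onset seizure frequency". SAP 5.9.3 fits an ANCOVA to the change in that quantity, with log-transformed baseline as covariate.

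Three percentages then follow:

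- **Versus placebo (5.9.3):** "The percent reduction relative to placebo and 90%CI will be constructed by exponentiating the LSMean difference and 90%CI". The formula is 100×[1 − exp(LSMean_CVL-865 − LSMean_Placebo)].
- **Within group (5.9.3):** "Estimated Mean % Change from Baseline=100*[1-exp(LSMean" (closing brackets follow).
- **Seizure rate over time (Table 11):** both percentages are "derived from back-transformed statistics the same way as described in Section 5.9.3".

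The estimand in SAP 5.9.2 stays on the log scale: "estimated mean difference between CVL-865 treated and placebo subjects in change from baseline in focal onset seizure frequency per week in logarithmic scale".

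Protocol 9.4.1 covers the same endpoint in two ways that disagree. Its sentence reads: "The percent reduction relative to placebo will be constructed by exponentiating the LSMean difference between each CVL-865 treatment group and placebo". Its displayed formula is 100×[exp(LSMean_placebo) − exp(LSMean_CVL-865)]/[exp(LSMean_placebo) − 1], which is not a function of the difference alone. The SAP follows the sentence and does not say that it departs from the formula. SAP section 6 does not mention it.

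**The concern.** Exponentiating a difference in ln(X+1) gives a ratio of (X+1). The SAP labels one minus that ratio as a percent reduction, for an endpoint named as seizure frequency, so readers will take it as a reduction in seizures. It is smaller than that, and the shortfall grows as the seizure rate falls.

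The quantities at stake are the headline percentage and 90% CI of a key secondary endpoint, the within-group percentages, and the by-visit percentages in Table 11. The shortfall depends on rate, so the subgroups planned in SAP 5.9.5 ("Low frequency= up to 20 seizures a week; High frequency = 21 and above") would show different percentages for the same true effect.

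**Working it through.** The plan states no numerical percent reduction for this endpoint, so there is no figure to reproduce. The check is algebra, followed by simulation.

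**Inputs from the documents.** X is in seizures per week (SAP 3.1.1). The response is change in ln(X+1), and the back-transforms are those of SAP 5.9.3. The entry floor is 8 seizures in the 8-week baseline, or 4 per 28 days historically; each equals 1 per week (Protocol 5.1, criteria 3 and 4). There are 40 evaluable subjects per arm (SAP 1.2).

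**Assumed.** The placebo Maintenance rate P, because the documents give no rate distribution.

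**Step 1, versus placebo.** Let Lp and Lc be the Maintenance LSMeans of ln(X+1), with P = exp(Lp) − 1 and A = exp(Lc) − 1.

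- SAP: 1 − (A+1)/(P+1) = (P−A)/(P+1) = [(P−A)/P] × [P/(P+1)]
- Protocol displayed formula: [(P+1) − (A+1)]/P = (P−A)/P

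For example, P = 1 and A = 0.7 (a 30% reduction) give 1 − 1.7/2 = 15% under the SAP and 0.3/1 = 30% under the protocol.

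| P per week | P/(P+1) | True 30% prints as | True 50% prints as |
|---|---|---|---|
| 1 | 0.50 | 15.0% | 25.0% |
| 2 | 0.67 | 20.0% | 33.3% |
| 5 | 0.83 | 25.0% | 41.7% |
| 10 | 0.91 | 27.3% | 45.5% |
| 20 | 0.95 | 28.6% | 47.6% |

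P is the back-transformed (geometric-type) mean. The arithmetic mean puts the factor too close to 1: in one simulated case it gave 0.79 against an actual 0.72.

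**Step 2, within group.** The same algebra gives a factor B/(B+1), with B the baseline rate. A fall from 2 to 1 per week, truly 50%, prints as 1 − 2/3 = 33.3%. A reduction also prints as positive under a label of percent change, which is a labelling point only.

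**Step 3, rates that vary between subjects.** The assumptions were lognormal subject rates with medians 1.5/2.5/5/10 per week and log-SD 0.7/0.9/1.0/1.0, Poisson counts over 8 weeks, and entry at 8 or more baseline seizures. Placebo change was 0% or −15%, within-subject log-SD was 0.3, and the true reduction was 30%. With up to 200,000 subjects per scenario:

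- SAP formula: 18.4–26.2%
- Protocol formula on Maintenance LSMeans: 28.7–29.2%
- ln(X+0.1) with the SAP's form: 28.8–29.8%

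The protocol formula is therefore close, but not exact, when rates vary.

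**Step 4, the 90% CI.** These are 4,000 trials of 40 per arm, with within-subject log-SD 0.5 and placebo −15%. Coverage of the true 30% was:

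| Median rate per week | SAP CI | Delta-method CI, protocol formula |
|---|---|---|
| 1.5 | 49.0% | 90.0% |
| 2.5 | 69.4% | 89.4% |
| 5 | 81.6% | 90.2% |
| 10 | 86.6% | 90.0% |

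A repeat with other simulation details gave SAP coverage of 43/64/77/85%.

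**Step 5, subgroups.** With 400,000 subjects, a true 30% in everyone, and cuts at 20 and 21 per week, the SAP formula gave the following at medians 2.5/5/10. Low frequency: 21.1/23.3/25.1%. High frequency: 28.6/29.5/29.3%. The gaps are 7.5, 6.2 and 4.2 points. The protocol formula gave 28.9–29.3% (low) and 30.1–30.7% (high).

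**Step 6, why restoring the −1 alone fails.** The SAP's LSMeans are of change, so exp(LSMean_placebo) is near 1 and falls below 1 if placebo improves. The denominator is then near zero or negative. With a 15% placebo improvement, change-score LSMeans in the protocol formula gave −99% to −163%. Because ln(B+1) is a covariate, modelling Maintenance ln(T+1) in place of the change shifts only the baseline slope, by 1. The LSMean difference and SE were identical to five decimals (for example −0.20286, SE 0.00141).

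**The case against.** The strongest reply is that nothing inferential is wrong. The estimand is the log-scale difference; that difference, its CI, its P-value and the RRatio are untouched. The trial is Phase 2, and SAP 5.4 calls it exploratory. The error pulls towards zero: with no true effect, the SAP's 90% CI covered in 89–91% of simulated trials, so it creates no false claim of benefit. All of this stands.

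Other planned outputs also limit the harm. The Poisson model of raw counts in SAP 5.9.6 gives a rate ratio with no added constant. Of the ln(X+0.1) rerun, SAP 5.9.4 says: "This sensitivity analysis is to assess if the correction for zero in seizure frequency may have undue effect on other low seizure frequencies". Its factor is P/(P+0.1), or 0.91 at P = 1. The rank test uses percent change on the original scale. An attentive reader would therefore see nearly unattenuated estimates elsewhere. None of these corrects the main percentage, and a main result that disagrees with its own sensitivity analyses for a purely algebraic reason invites misreading.

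The size is conditional. Nothing in the documents places this trial between P = 1 and P = 20, and the coverage figures depend on assumed variances and placebo change. SAP 5.9.5 plans no interaction test, and subgroup intervals would be wide compared with gaps of 4 to 8 points.

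Relabelling the output as a reduction in (weekly rate + 1) would also be honest, but that quantity has little clinical meaning.

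**Conclusion.** The concern holds. The factor P/(P+1) is exact for back-transformed LSMeans and approximate for the true seizure reduction when rates vary between subjects. The understatement is half at P = 1 per week, a third at 2, 17% at 5, 9% at 10 and 5% at 20, with P assumed throughout. The CI limits are pulled in to a similar degree. The fault reaches the comparison with placebo, the within-group figure, the 5.9.5 subgroups and Table 11. It does not reach any test. It should be fixed before database lock, as an error of scale and labelling in a key secondary result.

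**What to change.** In SAP 5.9.3:

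- Fit the ANCOVA to Maintenance ln(T+1), with treatment and ln(B+1) as covariate. The treatment difference, SE and P-value do not change.
- From those LSMeans, not the change-score LSMeans, report 100×[exp(LSM_placebo) − exp(LSM_CVL-865)]/[exp(LSM_placebo) − 1].
- For the 90% CI, apply the delta method to log{[exp(LSM_CVL-865) − 1]/[exp(LSM_placebo) − 1]} and exponentiate, or use a bootstrap.
- For within-group change, compare exp(LSM) − 1 at Maintenance with exp(overall mean of ln(B+1)) − 1 at baseline, with a bootstrap 90% CI. Call it percent reduction, or reverse the sign.
- Apply the same to the 5.9.5 subgroups and to seizure rate over time in Table 11.
- State whether the sentence or the displayed formula in Protocol 9.4.1 is followed.

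Keep the 5.9.4 analyses as sensitivity analyses and the 5.9.6 Poisson model as supplemental. The cost is SAP wording, a few lines of code and slightly more CI computation. Data, test and P-value are unchanged.

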5.9.4. Sensitivity Analyses

The sensitivity analyses to assess the impact of low eDiary compliance and that of discontinuation potentially related to treatment described in Section 5.8.4 for the primary estimand will also be performed for the key secondary efficacy estimand.

Two additional sensitivity analyses will be performed to assess the impact of the logarithmic transformation ln(X+1) of seizure frequency. The first one will be based on a slightly modified logarithmic transformation ln(X+0.1). This sensitivity analysis is to assess if the correction for zero in seizure frequency may have undue effect on other low seizure frequencies. In addition, the percent change from baseline in seizure frequency in Titration Phase and Maintenance Phase will also be analyzed using a nonparametric approach (in the original scale) of Wilcoxon rank sum test followed by the Mann-Whitney test for the comparison of each active treatment group to placebo.

5.9.5. Subgroup Analysis

The following subgroup analyses will be conducted:

- 1. subjects with baseline eDiary compliance $\geq 80\%$.
- 2. subgroup analysis of baseline disease characteristics based on seizure frequency, defined: Low frequency= up to 20 seizures a week; High frequency = 21 and above, including all subjects with "uncountable" seizures will be conducted.

5.9.6. Supplemental Analysis

A supplemental analysis will be conducted using a Poisson Regression model on the untransformed data for the raw number of seizures. A generalized linear model assuming a Poisson distribution and canonical log link function will be applied to the raw seizure count over the Maintenance Phase. The model will have an off-set parameter for the number of non-missing eDiary days (i.e., ln(days)) the subject was in the maintenance phase. Independent variables will include treatment and baseline seizure count.

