## 5.1 Inclusion Criteria

Subjects are eligible to be included in the trial only if all of the following criteria apply:

1.	Male and female subjects, ages 18 to 75 years, inclusive, at the time of signing the ICF.
2.	A diagnosis of epilepsy with focal onset (as defined in the 2017 ILAE Classification of Seizures [Fisher et al, 2017]), focal aware (except subjects with only focal aware seizures without a motor component), focal impaired awareness, and focal to bilateral tonic-clonic seizures for at least 2 years prior to signing the ICF. Diagnosis will be based on the investigator's assessment of available clinical, radiographic, and EEG data and the review by TESC.
3.	A history of an average of 4 or more spontaneous and observable focal onset (as defined in the 2017 ILAE Classification of Seizures [Fisher et al, 2017]), focal aware (except subjects with only focal aware seizures without a motor component), focal impaired awareness, and focal to bilateral tonic-clonic seizures per 28-day period for at least 3 months (84 days) prior to signing the ICF.
4.	A minimum of 8 focal onset (as defined in the 2017 ILAE Classification of Seizures [Fisher et al, 2017]), focal aware (except subjects with only focal aware seizures without a motor component), focal impaired awareness, or focal to bilateral tonic-clonic seizures during the 8-week Baseline Period with no 21-day period free of any of these seizure types.
5.	Subjects who have tried and failed at least 2 appropriate AEDs in the past.
6.	Subjects currently taking 1 to 3 permitted AEDs (see concomitant medication exclusions) at a stable dose for 4 weeks prior to the Screening Visit. VNS, DBS, and RNS is permitted and is not considered an AED. The VNS, DBS, and RNS settings should remain stable for 4 weeks prior to the Screening Visit. Note: Should a subject require a change of AED therapy/dose or VNS, DBS, or RNS settings between the Screening Visit and Visit 1, that subject should not continue in the trial at that time but must remain on the new regime for at least 4 weeks and then may repeat the screening process.
7.	An MRI or CT scan of the head within 10 years prior to Screening Visit to demonstrate no progressive structural abnormality. If a scan is not available, one should be conducted during the Baseline Period with a report that demonstrated no progressive structural abnormality available prior to randomization.
8.	BMI of 17.5 to 40.0 kg/m  and a total body weight $>50$ kg (110 lbs).

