1.2. Sample Size Considerations

Approximately 214 subjects will be screened to achieve 150 subjects randomly assigned to treatment (50 per group) and 120 evaluable subjects for an estimated total of 40 evaluable subjects per treatment group.

A sample size of 50 subjects per group (total of 150 subjects) will provide at least 80% power to detect a difference in the means of the primary outcome measure (RRatio) of -20 (PASS 2008 Tests of Two Means, Two Sample T-Test, 2-sided alpha level = 0.1, Standard Deviation=34, and a 20% dropout rate). Approximately 214 subjects will be screened to achieve 150 subjects randomized.

In the event of higher than anticipated early terminations due to COVID-19 or other reasons, Cerevel may extend enrollment in order to maintain the planned statistical power.

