5.2. Populations for Analyses

The analysis populations are defined Table 10.

Population	Description	Analysis
All Screened Subjects	All Screened Subjects includes all subjects who signed the informed consent form.	Disposition
ITT	All randomized subjects	Disposition, Demographic and Baseline Characteristics
FAS	All randomized subjects who receive at least 1 dose of IMP. This will be the safety analysis set.	Safety analysis
mITT	All randomized subjects who receive at least 1 dose of IMP and have both baseline seizure frequency recorded in the eDiary with entry compliance $\geq 20\%$ and at least 1 post baseline entry in the seizure diary during maintenance phase.	Primary analysis set for efficacy
PK Analysis Set	All randomized subjects who receive at least 1 dose of IMP and have at least 1 measurable CVL-865 concentration	PK analysis

Table 10:Populations for Analysis

Abbreviations: FAS = full analysis set, IMP = investigational medicinal product, ITT = intent-to-treat, mITT = modified intent-to-treat, PK = pharmacokinetic.

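### The supplemental Poisson model for seizure counts makes no allowance for overdispersion, so its standard errors would be too small and its 10% tests far too liberal

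*SAP*

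**What the plan says.** SAP 5.9.6 adds a count model to the first key secondary endpoint: "A generalized linear model assuming a Poisson distribution and canonical log link function will be applied to the raw seizure count" for the Maintenance Phase, with the log of the days that have diary data as offset. On covariates it says: "Independent variables will include treatment and baseline seizure count". That is the whole specification. Neither there nor elsewhere is there a scale parameter, robust variance, subject effect, negative binomial alternative or overdispersion check. Protocol 9.4.1 is shorter: "A secondary analysis of this endpoint will be conducted using a Poisson Regression model on the untransformed data". SAP 5.9.6 names no significance level, so the general two-sided 0.1 rule in Protocol 9.4 applies.

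Five other places bear on the point:

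- SAP 1.2 plans on "2-sided alpha level = 0.1, Standard Deviation=34, and a 20% dropout rate" for RRatio, with 40 evaluable subjects per arm.
- Protocol 5.1 (criterion 4) sets "A minimum of 8 focal onset" or related seizures over the 8-week baseline.
- SAP 5.9.3, the main model for this same endpoint, uses "the log-transformed baseline focal onset seizure frequency per week as a covariate".
- SAP 5.9.5 splits subjects as "Low frequency= up to 20 seizures a week; High frequency = 21 and above".
- SAP 5.2 admits to mITT subjects who "have both baseline seizure frequency recorded in the eDiary with entry compliance" of 20% or more.

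**The concern.** A Poisson model without a dispersion term treats each subject's count as having variance equal to its fitted mean. If subjects' rates vary more than that, the standard errors are too small, the intervals too narrow and the tests too liberal. A nominally significant benefit or harm could then easily appear for either dose with no true effect. The model could not usefully corroborate the ANCOVA in SAP 5.9.3.

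The covariate raises a second, smaller problem. A raw count under a log link makes expected Maintenance seizures exponential in baseline seizures, where proportionality is the natural expectation. The count is also not scaled for the number of baseline diary days.

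**Working it through.** **1. The plan's own figure.** With 40 per arm, difference 20, SD 34 and two-sided alpha 0.1, the standard error is 34 × √(2/40) = 7.60. Then 20/7.60 = 2.63, and Φ(2.63 − 1.645) = 83.8% (83.2% by noncentral t). The 50 randomized follow from 40/0.8. The stated power of at least 80% reproduces, so SD 34 is the variation the trial was planned on.

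**2. RRatio SD from Poisson noise alone.** For a stable subject rate, RRatio ≈ 50 × ln(T/B), so SD ≈ 50 × √(2/μ), where μ is the mean count per 8 weeks.

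| μ per 8 weeks | Approximate SD | Simulated SD (baseline at least 8) |
|---|---|---|
| 8 | 25.0 | 20.0 |
| 16 | 17.7 | 17.5 |
| 40 | 11.2 | 11.3 |
| 80 | 7.9 | 7.9 |

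With lognormal baseline rates (medians 1.2–4 per week, log-SD 0.6 or 0.9) the SD is about 13–20 with full diaries. It is 16–24 if 20% of subjects have only 1–55 Maintenance diary days. All of these are below 34.

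**3. Dispersion implied by SD 34.** If the variance is φ times the mean, 34 = 50 × √(2φ/μ), so φ = μ × 0.68²/2 = 0.231μ. Poisson standard errors are then too small by √φ, and a nominal 10% test has actual size 2 × [1 − Φ(1.645/√φ)].

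| μ | φ | √φ | Actual size |
|---|---|---|---|
| 8 | 1.85 | 1.36 | 23% |
| 16 | 3.70 | 1.92 | 39% |
| 40 | 9.25 | 3.04 | 59% |

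This leaves out differences between subjects that the baseline count does not capture.

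**4. Simulation with no treatment effect.** Three arms of 40; at least 8 baseline seizures in 56 days; Poisson counts given a lognormal subject rate; Maintenance rate equal to baseline rate times a lognormal change with log-SD τ. For SD 34, τ was 0.54–0.70 over 16 settings: four medians, two log-SDs, full or partly short diaries. Each setting had 1000 trials and two comparisons per trial.

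| Model, RRatio SD 34 | Rejection at nominal 10% |
|---|---|
| SAP 5.9.6 as written | 54–83% |
| Same, log baseline only | 52–82% |
| SAP model plus robust variance | 10–16% |
| Poisson, log baseline, robust variance | 10–15% |
| Negative binomial, log baseline, model-based SE | 12–17% |
| Negative binomial, log baseline, sandwich SE | 10–13% |

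For the model as written, Pearson dispersion was 6–38, standard errors were 2.7–8.1 times too small, and p < 0.001 occurred in 22–69% of comparisons. At RRatio SD 20–24 it still rejected in 40–75%.

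A second simulation, also calibrated to SD 34, put extra variation in both periods and used other baseline distributions. The model as written rejected in 45% (common mean 8), 54% (common mean 16) and 62% (median 16, log-SD 0.5), and in 77–87% with more skewed baselines. With one common rate and no extra variation the same code gave 7–10%, so in the common-rate settings the excess comes from overdispersion.

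**5. The raw baseline count.** Taking the entry minimum of 8 and 21 per week × 8 weeks = 168, the range is 21-fold. A slope that is proportional at both ends is ln(21)/160 = 0.0190. For a subject with 40 baseline seizures it predicts 8 × exp(0.0190 × 32) = 14.7. A subject with 20% baseline compliance (0.2 × 56 ≈ 11 days) can enter with a count 5 times smaller at the same weekly rate. With Poisson noise only, the raw-count model rejects in 25–69% of comparisons, against 21–26% with log baseline.

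**The case against.** - **Standing of the analysis.** It is supplemental, in a study the SAP calls exploratory, and no decision rule uses it. The checks in SAP 5.9.4, including the rank test, do not assume Poisson variance. This stands and limits the weight of the point.
- **The estimate survives.** If the mean model is right, overdispersion leaves the rate ratio consistent, so its direction and size can still be read. That is fair, but it does not rescue the intervals or p-values.
- **The size rests on assumptions.** The documents give no seizure-rate distribution, and moving from an RRatio SD to count dispersion is an inference. Milder settings give 45%, and the approximation gives 23% at the entry minimum, so 54% is not a floor. Poisson noise reached SD 34 only with every subject at mean 8, 40% with short diaries and the entry rule ignored. The direction is not in doubt.
- **The raw baseline adds little at SD 34.** This is correct: 54–83% becomes 52–82%. It dominates only when within-subject variation is small.
- **The covariate illustrations are stretched.** SAP 5.9.5 puts uncountable seizures in the High stratum, and SAP 3.1.1 counts a cluster episode as one event, so 168 is not a floor for that stratum. The 20% compliance case is a corner case, because 8 seizures would normally have to be recorded in about 11 days. The simulations shortened only Maintenance diaries and do not measure it.
- **The protocol names Poisson regression.** A negative binomial model would depart from Protocol 9.4.1. A robust variance on the Poisson model would not.

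**Conclusion.** The concern holds. Run as written, SAP 5.9.6 fixes the variance at the mean, while the plan's own SD of 34 points to counts well beyond Poisson. The nominal 10% test would have an actual size of roughly 45–87% across the simulated SD 34 settings, and about 23% in the mildest approximation. These figures assume 40 per arm and particular rate distributions; the direction does not depend on them. The raw-count covariate is a real but secondary defect.

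The practical impact is limited to this supplemental analysis. It should be corrected before unblinding, because a variance method chosen afterwards would look driven by the data.

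**What to change.** Replace the model text in SAP 5.9.6 with, for example:

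> Maintenance seizure counts will be analysed with a negative binomial model (log link, offset ln of non-missing Maintenance eDiary days) with treatment and ln of baseline weekly seizure frequency, using a robust (sandwich) variance. Rate ratios with 90% CIs will be reported.

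A Poisson model with the same terms and a robust variance is also acceptable, and it stays within the protocol's wording. The minimum change is to add the robust variance to the model as written; on its own that reached 20% rejection in skewed settings with little within-subject variation.

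The cost is one paragraph and a few program options, plus a recorded departure from Protocol 9.4.1 if the negative binomial is chosen. Intervals will be wider, and at 40 per arm the error rate will be close to nominal (about 10–15%) but not exact.
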